9.5 STUDY SIZE

Based on the result of study by Wedzicha JA, et al, [P16-05628] (where at least 25% of the patients in the Tio/Olo group have a first moderate or severe exacerbation at 127 days [95% CI, 107 to 149] and in ICS/LABA group at 87 days [95% CI, 81 to 103] (HR = 0.78, [95% CI 0.70 to 0.86])), we assume that at least 25% of patients in the ICS/LABA experienced a first moderate or severe COPD exacerbation at 103 days and the HR of Tio/Olo to LABA/ICS is 0.9. For a study duration of 6 years, a total of 4978 patients (2489 patients each arm) are needed to detect the difference between the two arms with 2-sided alpha of 0.05 and 90% power

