### 7.3 COVARIATES

Demographic characteristics and cohort entry information:

- Sex
- Age
- Calendar year of cohort entry
- Season of index date (winter, Dec-Feb; spring, Mar-May; summer, Jun-Aug; fall, Sep-Nov )

Additional characteristics will be defined during the 1-year pre-index baseline period:

- Previous COPD treatments
  - LAMA monotherapy
  - LABA monotherapy
  - ICS monotherapy
  - LAMA/ICS free combination therapy
- Use of other respiratory drugs
  - Mucolytics
  - Theophylline
  - Short-acting beta-agonists
  - Short-acting muscarinic antagonists
- Previous acute COPD exacerbation (measured both 12 months and in the 30 days prior to cohort entry), categorized as 0, 1, or 2+.
  - All exacerbations (Moderate+Severe)
  - An outpatient visit with a diagnosis code for COPD in any field + a prescription for an oral corticosteroid or an antibiotic for respiratory infections (Moderate); prescriptions within 30 days of each other were considered as continuation of the initial exacerbation.
  - Hospitalizations or emergency room visits with a primary diagnosis for COPD

(Severe); hospitalizations or emergency room visits within 30 days of each other were considered as continuation of the initial exacerbation.

- Hospitalizations caused by exacerbation of heart failure in 12 months prior to index date, categorized as
  - 0;
  - 1;
  - 2+.
- All-cause hospitalizations in 12 months prior to index date;
  - 0;
  - 1;
  - 2+.
- Comorbidities:
  - Cardiovascular disease
  - Cerebrovascular disease
  - Diabetes
  - Chronic kidney disease
  - Pneumonia
  - Cancer
  - Cirrhosis
- Charlson Comorbidity Index (CCI)
- History of medications dispensed in the 12 months before or on the index date will be identified from the pharmacy dispensing history:
  - Cardiovascular drugs:
    - antihypertensives;
    - antiarrhythmics;
    - nitrates;
    - heart failure medications
  - Lipid-lowering medications
  - Blood glucose-lowering medications
  - Anticoagulants and antiplatelet agents
  - Antibiotics
  - Antineoplastic agents
- COPD severity

The definition of the severity of COPD in this study was developed based on the information in previous studies, GOLD recommendations and clinical practice in Taiwan, see below. Patients who fulfil criteria for more than one category will be classified as being in the most severe category.

Operational definition of COPD severity:

- Mild:

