## **10. DATA ANALYSIS**

### **10.1 MAIN ANALYSIS**

All variables, including patient characteristics, baseline measures, and outcomes, will be analyzed descriptively.

- For all analyses, variables will be reported as follows: Continuous variables (e.g., age) will be presented as means (with standard deviation, SD) and/or medians (with interquartile range, IQR), minimum, maximum.

- Categorical variables (e.g., sex) will be presented as absolute and relative frequencies.

All analyses will be presented for each treatment group (Tio+Olo vs LABA/ICS) overall. We will first describe formation of the study cohort. Propensity score (PS) matching will be used to generate two comparable treatment groups. All covariates, except season of index date, will be used to estimate the propensity score with logistic regression. Patients in LABA/ICS group will be individually matched to patients in the Tio/Olo group with 1:1 ratio. A caliper of 0.06 standard deviation of logit (propensity score) will be used to define the range of estimated PS within which to select the comparator. Within that range the LABA/ICS patient with the closest estimated propensity score to the Tio/Olo patient will be selected.

Patient characteristics at baseline in patients treated with Tio+Olo and patients treated with LABA/ICS will be described separately using standard descriptive statistics after propensity score matching. Absolute standardized differences (ASDs) will be used to compare the characteristics between the two groups after propensity score matching, in which a  $>0.1$  ASD indicates a meaningful difference.

All the analyses for primary outcome and secondary outcomes will be performed on patients after propensity score matching. Baseline characteristic table shell are provided in [Table 1](#). The propensity score matching will be carried out once without re-matching.

For the analysis of the primary outcome, individuals will be followed up from the index date until the first moderate or severe COPD exacerbation. The data after the earliest date of the following event would be censored:

- 1) disenrollment
- 2) the end of the study period
- 3) death
- 4) discontinuation of index drug use (a lapse of 45 days without subsequent prescription)
- 5) switching from Tio/Olo to ICS/LABA or from ICS/LABA to Tio/Olo
- 6) escalation to triple therapies (ICS/LAMA/LABA free or fix dose combination)

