Note that per study protocol, switching from one ICS/LABA to another ICS/LABA is not a censoring event.

Univariate proportional hazard regression model will be used to compare the time to event between the two treatment groups. It will provide an estimate of the hazard ratio (HR) of time to the first moderate or severe COPD exacerbation associated with Tio+Olo use relative to LABA/ICS use, along with 95% CI. In the event that there are baseline covariates with unequal distribution between the treatment groups, defined as absolute standardized difference larger than 0.1, the covariate(s) will be included in a multiple regression model in addition to the exposure status (Tio/Olo or LABA/ICS).

The analysis of the secondary objectives related to time to triple therapy escalation and time to first hospitalization for community-acquired pneumonia will be univariate proportional hazard regression model with an as-treated approach, similar to that of the primary analysis. The estimate of hazard ratio (HR) of time to triple therapy escalation and first hospitalization for community-acquired pneumonia associated with Tio+Olo use relative to LABA/ICS use,

[figure not shown]
Proprietary confidential information © 2022 Boehringer Ingelheim International GmbH or one or more of its affiliated companies

along with 95% CI will be provided. For the analysis of these time-to-event outcomes, patients will be followed until the event of interest or earliest of the date of the follows, whichever happened first:

- 1) outcome event of interest;
- 2) disenrollment;
- 3) the end of the study period;
- 4) death;
- 5) discontinuation of index drug use (a lapse of 45 days without subsequent prescription)
- 6) switching from Tio/Olo to ICS/LABA or from ICS/LABA to Tio/Olo

In the event that there are baseline covariates with unequal distribution between the treatment groups, defined as absolute standardized difference larger than 0.1, the covariate(s) will be included in a multiple regression model in addition to the exposure status (Tio/Olo or LABA/ICS).

[figure not shown]
Proprietary confidential information © 2022 Boehringer Ingelheim International GmbH or one or more of its affiliated companies

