## ANNEX 1. ADDITIONAL INFORMATION

Table 1. Baseline characteristic of the study cohort

	Before propensity score match				After propensity score match			
	Tio/Olo cohort		ICS/LABA cohort		Tio/Olo cohort		ICS/LABA cohort	
	N	%	N	%	ASD	N	%	ASD
Gender								
Male								
Female								
Age								
40~54								
55~69								
70~84								
85+								
Calendar year of cohort entry								
2014								
2015								
2016								
2017								
2018								
2019								
Season of index date								
Spring (Mar-May)								
Summer (Jun-Aug)								
Fall (Sep-Nov)								
Winter (Dec-Feb)								
COPD treatments in 1 year prior to index date								
LAMA								
LABA								
ICS								
ICS+LAMA free combination								
Use of other respiratory drugs in 1 year prior to index date								
Mucolytics								
Theophylline								
Short-acting beta-agonists (SABA)								
Short-acting muscarinic antagonists (SAMA)								

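### Season of index date alone is left out of the propensity score without a reason, so matching does not secure balance on season; the likely bias is small and including it costs almost nothing

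*SAP*

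**What the plan says.** - SAP 7.3 defines the covariate with four levels: "Season of index date (winter, Dec-Feb; spring, Mar-May; summer, Jun-Aug; fall, Sep-Nov". The same list contains "Calendar year of cohort entry".
- SAP 10.1 builds the score from everything on that list but one: "All covariates, except season of index date, will be used to estimate the propensity score with logistic regression". No reason follows. Matching is 1:1, within a caliper of 0.06 SD of the logit, and is done once.
- Protocol 9.7.1 leaves the choice of score covariates to the SAP, so the two documents do not conflict on this.
- Balance is measured: "Absolute standardized differences (ASDs) will be used to compare the characteristics between the two groups after propensity score matching". The Table 1 shell in SAP Annex 1 has rows for "Season of index date".
- The primary and pneumonia models are univariate by default. Adjustment is conditional: "In the event that there are baseline covariates with unequal distribution between the treatment groups, defined as absolute standardized difference larger than 0.1" leads to the covariate being added to a multiple regression model. Table 2 has a place for an adjusted HR.

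**The concern.** Season of starting is known for every patient and is a plausible predictor of respiratory exacerbation and pneumonia admission, both of which are outcomes here. The primary event can come early: Protocol 9.5 assumes that 25% of comparator patients "experienced a first moderate or severe COPD exacerbation at 103 days", which is roughly one season. Calendar year in the score does not balance season within a year.

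If starts of the two treatments fall differently across the seasons, neither the matching nor the default model removes the difference unless it passes the trigger, "absolute standardized difference larger than 0.1". The planned effect is modest (HR 0.9), so even a modest avoidable bias deserves a look.

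**Working it through.** The plan gives no figure for season, so there is none to reproduce. The check asks how far the HR could move at the largest imbalance the plan leaves unadjusted.

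**1. Largest unadjusted imbalance.** Assume 25% winter starts in one arm. Solve (q − 0.25) / √{[q(1 − q) + 0.25 × 0.75]/2} = 0.1. This gives q = 0.294, or 0.208 in the other direction.

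**2. Can chance alone produce it?** With 2489 per arm (Protocol 9.5) and season unrelated to treatment, the SE of the ASD is √(2/2489) = 0.028. The probability of |ASD| > 0.1 is about 0.0004. A relevant imbalance therefore needs a systematic difference between arms.

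**3. Crude upper figure.** If a winter *start* raised the hazard r-fold for the whole of follow-up, the factor on the HR would be (1 + 0.294(r − 1)) / (1 + 0.25(r − 1)). This is 1.012, 1.020 and 1.036 for r = 1.3, 1.5 and 2.0.

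**4. Does starting season fix the season at risk?** From 25% at 103 days, with exponential times:
- hazard = −ln(0.75)/103 = 0.00279 per day;
- median = ln 2/0.00279 ≈ 248 days, more than two seasons;
- events in the first 90 days = 1 − exp(−0.00279 × 90) = 22%.

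Most events therefore fall outside the starting season unless treatment stops early. Step 3 overstates the effect.

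**5. Season effect placed in calendar time.** The hazard is multiplied by r in December to February (90 of 365 days) and scaled so that its yearly mean stays 0.00279. For r = 2 the non-winter hazard is 0.00279/(1 + 90/365) = 0.00224. Other inputs:
- true HR 0.90 and six years of follow-up;
- winter starts 29.4% v 25.0%, with the rest spread equally over the other three seasons;
- exponential discontinuation with an assumed median (the documents give none).

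With e₁, e₀ the expected events and n₁, n₀ the expected numbers at risk on each day, the Cox score equation Σ[e₁ − (e₀ + e₁)·b·n₁/(n₀ + b·n₁)] = 0 is solved for b. The factor is b with unequal season shares divided by b with equal shares.

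| Winter hazard r | No discontinuation | Median 365 d | 180 d | 90 d | 45 d |
|---|---|---|---|---|---|
| 1.3 | 1.0002 | 1.0005 | 1.001 | 1.002 | 1.004 |
| 1.5 | 1.0003 | 1.0008 | 1.002 | 1.003 | 1.007 |
| 2.0 | 1.0005 | 1.0015 | 1.003 | 1.006 | 1.0125 |

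The top value is 1.0126, about 1.013, if the true HR is 1. With 20.8% v 25.0% the factors run from 0.9998 to 0.988.

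**6. What that means for the planned effect.** 0.90 × 1.013 = 0.912. On the log scale, ln(1.013)/|ln 0.9| = 0.0129/0.1054 = 12% of the effect; at a factor of 1.0005 it is 0.5%. Events for HR 0.9, two-sided 0.05 and 90% power by Schoenfeld's formula are 3787. At HR 0.912, power is Φ(√(3787/4) × |ln 0.912| − 1.96) ≈ 81%; at a factor of 1.0005 it stays at about 90%.

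**7. A harsher arrangement.** Suppose winter and fall starts are both over-represented (29.2% each v 25%) and spring and summer are both 20.8%, so every level is at about ASD 0.1. With doubled winter hazard the factor is 1.005 with no discontinuation, 1.019 at a median of 90 days and 1.027 at 45 days. This needs all four seasons to be unfavourable at once.

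**The case against.** The strongest reply is that the plan does not ignore season. It tabulates season, measures balance and adjusts when the ASD exceeds 0.1. **This stands.** A reader might infer from the omission that the matched groups will be unbalanced on winter starts. The documents do not support that: balance is an empirical result, and leaving season out creates no imbalance unless starts differ systematically by arm.

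A reader might suspect such a difference from uptake of a newly covered product. SAP 9.3 mentions years in which Tio/Olo was not covered, but gives no coverage date or uptake pattern. Under linear uptake within one year, fall starts would rise to about 40% and winter starts would *drop* to about 19%. That effect would be diluted in the pooled cohort.

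A reader might also take the factor 1.036 in step 3 as the likely bias, about a third of the planned effect. That requires a doubled hazard throughout follow-up for anyone who started in winter, which does not fit the plan's own event rate (step 4).

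Further safeguards may exist out of sight. The SAP contents list redacts the entry between 10.1 and 10.3, and the protocol checklist cites stratified analyses in a section 9.7.2 that is not in the text available.

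What remains is that one listed covariate is singled out for omission, no reason is given, and the visible backstop acts only above 0.1. The SAP also does not say how the ASD is computed for a four-level variable, or which HR is primary once adjustment is triggered.

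**Conclusion.** The point holds as a minor, nearly free improvement. Matching does not secure balance on season, and an imbalance with ASD up to 0.1 is handled neither by the score nor by the visible default model for the primary and pneumonia HRs.

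The expected bias is small: a factor of about 1.0002 to 1.013 on the exacerbation HR, in either direction, with 29.4% v 25.0% winter starts. Only the deliberately adverse four-season pattern with very early discontinuation reaches 1.027. The season shares, the winter hazard (1.3 to 2.0) and the discontinuation times are all assumptions. The plan supplies only the 103-day event rate, the HR of 0.9, the six-year duration and the ASD threshold. The pneumonia HR was not modelled, because the documents give no event rate for it.

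**What to change.** In SAP 10.1, delete the exception for season and enter season of index date in the propensity model as a four-level main effect. Do not cross it with calendar year. Winter is December to February, so a year-by-winter cell would join January and February to the following December and would not be a calendar quarter. The crossing would also add up to 18 terms (3 main, 15 interaction) and leave cells with no Tio/Olo patients in years without coverage.

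If the sponsor prefers to keep the exclusion, the SAP should give the reason. In either case, two short clarifications would help: whether the ASD for a multi-level covariate is taken per level or overall, and which HR is primary when adjustment is triggered. The statement in Protocol 9.7.1 that other known predictors enter the Cox model should also be reconciled with the univariate default in the SAP.

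The cost is one phrase and three model terms, with no new data. Any loss of matches under the 0.06 SD caliper is expected to be small but has not been shown.

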9.2.2 Study population

Inclusion criteria:

- At least oneprescriptions for Tio/Olo combined inhaler or a LABA/ICS combined inhaler between 1st January 2014 and 31st December 2019.
 - a) The first dispensing of either Tio/Olo or LABA/ICS combined inhaler will be defined as the index date;
 - b) For the main analyses, only fixed dose combination (FDC) inhalers will be included.
- 2. Aged \geq 40 years on the index date
- 3. At least one diagnosis of COPD at any time prior to or on the index date;
- At least one year of continuous medical and health insurance plan prior to the index date will be required to allow for a look-back period for the covariates and identification of new use of the study drugs;
- 5. At least one record in the health insurance system database;

Exclusion criteria:

- 1. Any use of Tio/Olo, ICS/LABA, or ICS/LAMA/LABA in free or fixed form for one year prior to the index date;
- Individuals with asthma, allergic rhinitis, lung cancer, interstitial lung disease, or lung transplant identified at any time prior to the index date

NIS Protocol Page 24 of 48 BI Study Number: 1237-0110 c38660249-01

Proprietary confidential information © 2022 Boehringer Ingelheim International GmbH or one or more of its affiliated

For the analysis of the primary outcome, individuals will be followed up from the index date until the earliest of the date of: the follows, whichever first 1) moderate or severe COPD exacerbation; 2) disenrollment; 3) the end of the study period; 4) death; 5) discontinuation of the index drug use as a lapse of 1.5 months without subsequent prescription (except for switching from the index ICS/LABA to a different ICS/LABA); 6) adding ICS mono on top of Tio/Olo, or adding LAMA momo on top of the index ICS/LABA

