9.7.1 Main analysis

All variables, including patient characteristics, baseline measures, and outcomes, will be analyzed descriptively.

- For all analyses, variables will be reported as follows: Continuous variables (e.g., age) will be presented as means (with standard deviation, SD) and/or medians (with interquartile range, IQR), minimum, maximum.
- Categorical variables (e.g., sex) will be presented as absolute and relative frequencies.

All analyses will be presented for each treatment group (Tio+Olo vs LABA/ICS) overall. We will first describe formation of the study cohort. Propensity score matching will be used to balance the baseline characteristics of patients in the two treatment groups. The covariates used to calculate the propensity score would be specified in the SEAP. All the analyses will be performed on patients after propensity score matching. Patient characteristics at baseline in patients treated with Tio+Olo and patients treated with LABA/ICS will be described separately using standard descriptive statistics after propensity score matching. Absolute standardized differences (ASDs) will be used to compare the characteristics between the two

NIS Protocol Page 30 of 48 BI Study Number: 1237-0110 c38660249-01

Proprietary confidential information © 2022 Boehringer Ingelheim International GmbH or one or more of its affiliated

groups after propensity score matching, in which a >0.1 ASD indicates a meaningful difference.

For the analysis of the primary outcome, individuals will be followed up from the index date until the first moderate or severe COPD exacerbation. The data after the earliest date of the following would be censored: 1) disenrollment; 2) the end of the study period; 3) death; 4) discontinuation of the index drug (except for switching from the index ICS/LABA to a different ICS/LABA); 5) escalation to triple therapies (ICS/LAMA/LABA free or fix dose combination). Cox proportional hazard regression model will be used to compare the time to event between the two treatment groups, while accounting for the potential baseline differences between them. Other known predictors will also be included in the model as covariates. It will provide an estimate of the hazard ratio (HR) of time to the first moderate or severe COPD exacerbation associated with Tio+Olo use relative to LABA/ICS use, along with 95% confidence intervals (CI). The analysis will be on-treatment.

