## **7. VARIABLES**

### **7.1 EXPOSURES**

Exposure of this study is defined as new initiation of Tio/Olo or ICS/LABA (FDC) during the study period. Detailed drug codes are provided in the Annex.

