### **(1). Time to triple therapy escalation after index date**

Triple therapy escalation, defined as any LAMA/LABA/ICS fixed dose combination or any concurrent use for 30 consecutive days of the following:

- a. any LAMA/LABA fixed dose combination + any ICS single formulation
- b. any LAMA single formulation + any LABA/ICS fixed dose combination
- c. any LAMA single formulation + any LABA single formulation + any ICS single formulation

The event date will be the 30th day after initiation of triple therapy.

As time-to-event data, the analysis will be univariate proportional hazard regression analysis to estimate the hazard ratio (Tio/Olo vs. comparator) and its 95% CI.

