## Appendix 3. COPD medications

Groups	Drug name	ATC code
LAMA	Tiotropium bromide	R03BB04
	Glycopyrrolate	R03BB06
	Umeclidinium	R03BB07
LABA	Salmeterol	R03AC12
	Formoterol	R03AC13
	Procaterol	R03AC16
	Indacaterol	R03AC18
	Olodaterol	R03AC19
ICS	Beclometasone(=beclomethasone)	R03BA01
	Budesonide	R03BA02
	Fluticasone	R03BA05
	Ciclesonide	R03BA08
ICS/LABA	Salmeterol and Fluticasone	R03AK06
	Formoterol and Budesonide	R03AK07
	Formoterol and Beclometasone	R03AK08
	Vilanterol and Fluticasone furoate	R03AK10
	Formoterol and Fluticasone	R03AK11
LABA/LAMA	Vilanterol and Umeclidinium bromide	R03AL03
	Indacaterol and Glycopyrronium bromide	R03AL04
	Olodaterol and Tiotropium bromide	R03AL06
LABA/LAMA/ICS	Vilanterol, Umeclidinium bromide and Fluticasone furoate	R03AL08
	Formoterol, Glycopyrronium bromide and Beclometasone	R03AL09

Proprietary confidential information © 2022 Boehringer Ingelheim International GmbH or one or more of its affiliated companies

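### A change to a non-study LAMA/LABA inhaler is cut only by the 45-day lapse, within-class product changes end follow-up in one arm only, and the triple-therapy definition omits one pairing

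*SAP*

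**What the plan says.** **Exposure.** SAP 7.1: "Exposure of this study is defined as new initiation of Tio/Olo or ICS/LABA (FDC) during the study period". One arm is a single product. The other is a class with five codes in SAP Appendix 3.

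**Switching.** The primary list in SAP 10.1 censors at "switching from Tio/Olo to ICS/LABA or from ICS/LABA to Tio/Olo". The same item stands in the list for the secondary time-to-event outcomes and in the list for rescue prescriptions. SAP 10.1 adds that "switching from one ICS/LABA to another ICS/LABA is not a censoring event". There is no counterpart for LAMA/LABA products.

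**Discontinuation.** All three lists also end follow-up at "discontinuation of index drug use (a lapse of 45 days without subsequent prescription". Protocol 9.2.2 has "discontinuation of the index drug use as a lapse of 1.5 months without subsequent prescription". Protocol 9.7.1 has no separate switch item and attaches the exemption to discontinuation: "discontinuation of the index drug (except for switching from the index ICS/LABA to a different ICS/LABA".

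**Other LAMA/LABA inhalers.** Besides Tio/Olo (R03AL06), SAP Appendix 3 lists "Vilanterol and Umeclidinium bromide" (R03AL03) and the indacaterol/glycopyrronium combination (R03AL04).

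**Triple therapy.** SAP 7.2.2 (1) and (2) count any triple fixed combination, or 30 consecutive days of concurrent use of one of three pairings: (a) "any LAMA/LABA fixed dose combination + any ICS single formulation"; (b) a single LAMA with an ICS/LABA fixed combination; (c) the three components singly. The event date is day 30. Item 6 of the primary list names escalation to triple therapy, free or fixed, without pointing to this definition.

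**The concern.** Three things follow from the wording.

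1. A direct crossover between the study treatments is cut at the switch. A move to a non-study LAMA/LABA waits for the lapse. At entry, by contrast, SAP 6.3 excludes prior use of any LAMA/LABA. Exacerbations on a drug that neither arm is meant to represent could be attributed to the index drug.
2. A patient who changes ICS/LABA product stays in follow-up. A patient who changes from Tio/Olo to another LAMA/LABA leaves it. If patients with poor control change product more often, the Tio/Olo arm loses its higher-risk patients and the comparator keeps them, which would lower the Tio/Olo hazard. Matching on baseline covariates does not remove a selection that arises after the index date.
3. A LAMA/LABA fixed combination taken with an ICS/LABA fixed combination contains all three components but fits none of pairings a to c. Followed literally, two secondary outcomes miss it.

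**Working it through.** The documents give no switching or product-change rate, so there is no plan figure to reproduce. The sample size of 4978 does not enter this point.

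**Step 1. Which rule catches a change of inhaler (SAP 10.1)?**

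| Change | Rule that applies | Follow-up ends |
|---|---|---|
| ICS/LABA to Tio/Olo, or the reverse | switch item | at the switch |
| ICS/LABA to R03AL03 or R03AL04 | discontinuation only | through the 45-day lapse |
| Tio/Olo to R03AL03 or R03AL04 | discontinuation only | through the 45-day lapse |
| one ICS/LABA to another | exempt | it continues |

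A non-study LAMA/LABA taken alone is not triple therapy, so item 6 does not apply in rows 2 and 3.

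**Step 2. Which rule catches an added inhaler?**

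| Situation | Pairings a to c | Consequence in the triple-therapy outcomes |
|---|---|---|
| ICS/LABA continued, R03AL03 or R03AL04 added | not met | no lapse, no named switch: not counted, follow-up continues |
| Tio/Olo continued, ICS/LABA added | not met | may be read as a switch and censored instead of counted |
| ICS/LABA continued, Tio/Olo added | not met | the same |

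The SAP does not say whether a switch requires the index drug to stop.

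**Step 3. How much can the lapse carry?** Inputs from Protocol 9.5: 25% of ICS/LABA patients with an event by day 103, hazard ratio 0.9. Assumptions: constant hazard, the same hazard on the new inhaler, the full 45 days counted.

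- Hazard: −ln(0.75)/103 = 0.002793 per day; × 365.25 = 1.020 per year.
- ICS/LABA: 1 − 0.75^(45/103) = 11.8%.
- Tio/Olo: 1 − 0.75^(0.9 × 45/103) = 10.7%.

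These are probabilities for a patient who changes, not for the whole arm. If a fraction q of the ICS/LABA arm changes in this way, at most about 0.118q of that arm has an event wrongly attributed. If the censoring date is the start of the lapse, the carry-over largely disappears. The SAP also does not say whether the lapse runs from the prescription date or from the end of supply.

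**Step 4. Illustration of the one-sided censoring.** Every input except the hazard is an assumption: true hazard ratio 1; gamma frailty Z with mean 1 and variance v; event hazard λZ with λ = 1.020 per year; product-change rate κZ censoring the Tio/Olo arm only, with no lag; background discontinuation δ per year in both arms; uniform entry over 6 years. With L(s) = (1 + vs)^(−1/v), the share at risk at time t is L(λt)·e^(−δt)·(1 − t/6) in the ICS/LABA arm, and the same with L((λ + κ)t) in the Tio/Olo arm. Solving the large-sample Cox score equation gives these hazard ratios (v = 0.5 / v = 1.0):

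| κ per year | δ = 0 | δ = 1 |
|---|---|---|
| 0.1 | 0.977 / 0.966 | 0.985 / 0.977 |
| 0.2 | 0.955 / 0.935 | 0.971 / 0.955 |
| 0.4 | 0.918 / 0.882 | 0.946 / 0.917 |

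At δ = 2 and κ = 0.4 the values are 0.958 / 0.934. Against the planned ln(0.90) = −0.1054, the range runs from ln(0.985)/ln(0.90) = 14% to ln(0.882)/ln(0.90) = 119%. A range that wide shows only that the answer depends on rates that the documents do not give.

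**The case against.** Four stronger readings are tempting, and the documents do not support them.

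- *A move to another LAMA/LABA is never censored.* The discontinuation item refers to use of the index drug and therefore ends follow-up after the lapse. What remains is the carry-over within the lapse.
- *Triple therapy can count as ICS/LABA without limit in the primary analysis.* Pairings a to c stand under the secondary outcomes. Item 6 of the primary list speaks generally of free or fixed triple therapy, and on plain reading two inhalers that together contain all three components are a free combination. The gap is firm only for the two triple-therapy secondary outcomes. The documents give no sign that the pairing is common.
- *The asymmetry is an error, or the two documents contradict each other.* Someone who changes ICS/LABA product is still on the comparator, while someone who leaves Tio/Olo for another LAMA/LABA is no longer on Tio/Olo. The Protocol prespecifies the exemption and the SAP follows it. This objection stands: it is a bias risk, not a mistake.
- *The bias has a known size.* It rests on unstated switching and discontinuation rates, and on the assumption that product change tracks exacerbation risk.

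In addition, the SAP contents show a redacted entry between 10.1 and 10.3. A sensitivity analysis of switching may be there, so its absence cannot be asserted.

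**Conclusion.** The point holds as a clarification that is cheap to make. The switch item leaves out two LAMA/LABA inhalers that the SAP itself lists, so a change to them is cut later than a direct crossover, by up to 45 days if censoring falls at the end of the lapse. The effect is limited to patients who make such a change, at an event probability of about 11% to 12% each under the design hazard. Different handling of within-class changes follows from comparing one product with a class. It may cause differential informative censoring, whose direction depends on who changes product and whose size cannot be computed from the documents. The omission in the triple-therapy definition is a plain gap for two secondary outcomes, and it can turn an escalation in the Tio/Olo arm into a censored switch.

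**What to change.** 1. **Switch item, all three lists in SAP 10.1.** Censor on the dispensing date at the first change to any dual fixed combination of the other class (ICS/LABA index: R03AL03, R03AL04 or R03AL06; Tio/Olo index: any ICS/LABA) or, in the Tio/Olo arm, to a non-index LAMA/LABA. State that a product added to a continuing index drug is assessed under the triple-therapy definition and not as a switch. Otherwise censoring at dispensing would come before the 30-day requirement can be met. For the lapse, state when it starts and which date is the censoring date.
2. **Triple-therapy definition, SAP 7.2.2 (1) and (2).** Add concurrent use of a LAMA/LABA and an ICS/LABA fixed combination, and refer item 6 of the primary list to this definition.
3. **Sensitivity analysis.** Report the primary hazard ratio also with the first change of index product censored in both arms, unless the redacted section already does so.

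Change 1 removes carry-over only. It keeps the asymmetry and can leave the hazard ratio no closer to 1. In a simulation with 400,000 patients per arm, 0.4 changes and 1 background discontinuation per year and a true hazard ratio of 1, the estimate was 0.951 / 0.936 (frailty variance 0.5 / 1.0) with the 45-day lag and 0.943 / 0.915 without it. Change 3 is the one that tests the asymmetry.

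The cost is SAP wording and one more run of the same Cox model, with slightly less follow-up in that run.
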